6.7 Measles vaccine and aerosol delivery device accountability

The investigator will assign a nurse to be responsible for vaccine and aerosol device storage and accountability at the trial site. The investigator/designated person will:

- Store the vaccine and device in the condition that has been specified in writing by the Sponsor in SOP WHO 4/1 and in accordance with the protocol and Indian regulatory requirements.
- Ensure that the vaccine storage temperature is maintained as specified in the protocol. There will be a daily temperature log. (SOP WHO 4/1)
- Maintain records of the vaccine and device delivery, inventory and return. (SOP WHO 4/1)
- Maintain up to date accountability on the vaccine and device accountability log. (SOP WHO 4/1)
- Ensure that the vaccine and device are used only in accordance with the approved protocol.

Written records of receipt and storage of the vaccine and devices, including date received, lot number, quantity received, and dose administered, with the coded identification of the subject, will be recorded. Any known discrepancies in the accountability of the vaccine will be documented. The investigator will not use the vaccine and/or devices in any other manner than that provided for in the protocol.

6.7.1.1 Vaccine Storage, Handling and Transport

The vaccine will be stored, according to the manufacturer's recommendations at $2^{\circ}C$ to $8^{\circ}C$ in a refrigerator in which the temperature is monitored and logged at least once a day. The refrigerator will be secured and located in a limited access area.

6.7.2 Policy and procedure for handling unused investigational product.

(SOP WHO 4/1))

- All unused un-reconstituted measles vaccine will be disposed of according to the manufacturers instructions and WHO³³.
- All reconstituted vaccine not used within 6 hours after reconstitution during an immunization session will be discarded according to WHO recommendations for multi dose open vials.⁴¹ Records will be kept of discarded vaccine.
- All non-reusable components of the nebulizer will be disposed of as indicated in SOP NEK 2/1
- The nebulizers used during the trial will be returned to the sponsor at the end of the trial according to sponsor-defined procedures.

6.8 Maintenance of trial randomization codes and procedures for breaking codes

6.8.1 Unblinding of laboratory specimens

Laboratory specimens collected up to day 91 will be unblinded by the designated Sub-Investigator (in charge of data Management and Statistics) at the start of the statistical analysis of the primary outcome and after the database has been locked (see SOP VEL 2/1).

Premature unblinding will be reported immediately to the clinical monitor and the Sponsor and will be documented in the investigator's file. The reason for premature unblinding of the samples should be given.

6.9 Source data

The following documents will be considered source data for this trial:

- Electronic audited copies of the Case Reports Forms and Adverse Events (AE) Investigation Forms
- In addition, the following original documents, data, and records will be considered as source documents:
- hospital records,
- o clinical and office charts,
- o laboratory notes, memoranda,
- pharmacy dispensing records,
- o recorded data from automated instruments,
- o copies or transcriptions certified after verification as being accurate copies,
- photographic negatives or files,
- o X-rays,
- o subject medical files, and
- records kept at the pharmacy, at the laboratories, and at medico-laboratory departments involved in the clinical trial).

7 Selection and withdrawal of subjects

7.1 Inclusion criteria

- Age: from 9.00 to 11.99 months on expected vaccination date;
- Resident in the study area and likely to remain for the duration of the child's involvement in the study;
- Parent/guardian willing for child to be randomized and willing for child to be followed up for at least 91 days (364 days for Vadu subset).

7.2 Exclusion criteria

- Having received measles, measles-rubella or measles-mumps-rubella vaccine (with confirmation from vaccination card).
- Any contraindication to measles vaccine administration as stated in the WHO measles vaccine position paper: ⁴²
 - Persons with a history of an anaphylactic reaction to neomycin, gelatine or other components the vaccine should not be vaccinated.
 - Furthermore, measles vaccine is contraindicated in persons who are severely immunocompromised as a result of congenital disease, HIV infection, advanced leukaemia or lymphoma, serious malignant disease, or treatment with high-dose steroids, alkylating agents or antimetabolites, or in persons who are receiving immunosuppressive therapeutic radiation.
 - Administration of immunoglobulins or other antibody-containing blood products may interfere with the immune response to the vaccine. Vaccination should be delayed for 3–11 months after administration of blood or blood products, depending on the dose of measles antibody. Following measles vaccination, administration of such blood products should be avoided for 2 weeks, if possible.
 - Mild, concurrent infections are not considered a contraindication, and there is no evidence that measles vaccination exacerbates tuberculosis. However, vaccination should be avoided if there is high fever or other signs of serious disease.

7.3 Subject withdrawal/discontinuation criteria

- Withdrawal of consent;
- Serious adverse event;
- Any other situation in which the Principal Investigator finds it in the subject's best interest to no longer continue his/her participation in the study.

If this occurs, the subject will be asked to continue with the clinical follow up as per the study protocol but would be excluded from the analysis. Withdrawn subjects will not be replaced.

See section 6.6.

8 Treatment of subjects

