6.2.2 Safety

6.2.2.1 Primary outcome

Adverse events up to and including day 91 post-vaccination;

Adverse events include acute clinical reactogenicity, other adverse events, and serious or unexpected adverse events.

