11.1.1 Analysis sets

- Primary analysis: per protocol (infants receiving the allocated vaccine and available for follow up at 91 days post-vaccination). For non-inferiority hypothesis, this is the conservative analysis;
- Secondary analysis: intent-to-treat analysis (all infants randomized, analysed in the group to which they were allocated, irrespective of intervention received) of primary and secondary outcomes.

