11.1.3 Statistical methods, safety

- Primary analysis: proportion (with 95% CI) with any adverse events in aerosol group and in subcutaneous group;
- Secondary analysis: proportions (with 95% CI) of individual adverse events.

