12.1.3 Safety

Primary analysis is proportion (95% CI) with any adverse events in aerosol group with subcutaneous group;

Secondary analysis will describe frequencies of individual adverse events (proportions with 95% CI).

An interim analysis of safety data will be completed. For this analysis, the DSMB will use data from the first 100 children in each arm to complete 91 days of follow up. This will be done as soon as possible after these data are available.

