In Figure 11.1.1 non inferiority has been demonstrated for scenarios 1), 2) and 3) since the lower limit of the 95% CI is above -5%. In addition for scenario 3) superiority has been shown because the lower limit does not include 0%. For scenarios 4) and 5) non-inferiority has not been demonstrated and for scenario 5) aerosol is inferior as the upper limit does not include 0%.

Note: Using the Wilson score method, 95% CI will be calculated using SAS software. (Newcombe 1998, Agresti et al 1998)

11.2 Per-Protocol (PP) Analysis Set:

This is the analysis set that will be used for the primary analysis of efficacy. The PP analysis set includes all children with an interpretable result from the blood sample scheduled for 91 days (-7 to +28 days), and without major protocol deviations. Study participants remain in the study up to until the point at which they drop-out or deviate from the protocol (Protocol section 12.0).

Protocol deviations include:

- Study participant incorrectly entered the study, e.g. did not meet age criteria;
- Study participant should have been withdrawn during study but was not;
- Study participant did not receive the vaccine according to the arm to which he / she was randomized;
- Study participant received the wrong dose of vaccine;
- Study participant received a dose beyond the recommended multi-dose vial policy
- Wrong subject ID randomized
- Wrong Subject ID
- Home Visit and Clinic visit on same date
- Visits outside the window period
- Wrong labelling of the CRF
- Wrong labelling of vials
- Informed consent issue

The assessment of long-term immunogenicity in the subset of participants from Vadu, includes children with an, interpretable result from blood sample scheduled for 364 days (-7 to +28 days), and without major protocol deviations.

11.3 Modified Intention to Treat (ITT) Analysis Set:

The 'intention to treat' analysis will be conducted as a secondary analysis. In a noninferiority trial such as this, the intention to treat analysis is more likely than the perprotocol analysis to give a type I error (falsely claiming non-inferiority) because this kind of analysis tends to minimize differences between the two treatments (1).

The ITT analysis set includes assessments up to 91 days (-7 to +28 days) post-vaccination. All study participants will be included in the group to which they were randomized.

SOP VEL 1/1:	Statistical Analysis Plan	Page 9 of 61
September 11, 2012		

11.4 As Treated Cohort Analysis set:

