The primary efficacy analysis for safety includes all children vaccinated, according to the route of vaccination that they received and with at least one safety assessment.

In addition, we will summarize explicitly any severe reactions or serious adverse events (SAE) in children vaccinated by the wrong route.

11.5 Timing of Analyses:

The primary efficacy analysis will be conducted after the last enrolled participant completes the day 91 follow up visit.

Every 3 months the data will be analyzed and a report will be made available for the DSMB. This report will focus on safety.

11.6 Method for Handling Missing Data:

For the primary efficacy analysis there is no plan to impute data values for participants who do not complete follow up visits.

For the PP dataset, missing values will be treated as missing at random. However, preliminary analyses such as age, sex, baseline immunogenicity distribution will be studied between the two groups to examine the validity of this assumption.

For the assessment of immunogenicity, missing values (e.g. no blood taken) are treated as if they are missing at random. The OD values for blood samples taken outside the specified time limits will be treated as missing values.

Note that missing values at 91 days post-vaccination and at other time points will be considered for further analyses. The missing information will be handled by best and worst case scenario methods. Where blood specimens are taken outside the recommended time interval, these results will still be used.

11.7 Significance Level:

This is a non-inferiority trial and the confidence interval approach will be used to determine the trial outcome. For additional analyses, such as those adjusting for covariates, we will not use a fixed 'statistical significance' level for reasons described by Sterne and Davey Smith (3). For analyses that require the calculation of p values, we will base our interpretation on examination of the effect size, confidence interval and p value.

11.8 Safety:

We will estimate the proportions (with 95% CI) of AE in each arm according to the definitions of the primary and secondary safety outcomes (Refer section 8.7 in the protocol).

SOP VEL 1/1:	Statistical Analysis Plan	Page 10 of 61
September 11, 2012		

11.9 Covariates to be examined:

Covariates of interest are as follows:

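### Protocol 7.3 excludes children withdrawn for a serious adverse event from an unspecified analysis, contradicting the protocol's own safety outcome and ITT set and SAP 11.4

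*Supplement*

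**What the plan says.** Protocol 7.3 gives three withdrawal criteria. One is "Serious adverse event", with no qualifier for causality or arm. If a criterion is met, "the subject will be asked to continue with the clinical follow up as per the study protocol but would be excluded from the analysis".

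Elsewhere the documents say:

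- Protocol 6.2.2.1, primary safety outcome to day 91: "Adverse events include acute clinical reactogenicity, other adverse events, and serious or unexpected adverse events".
- Protocol 11.1.3, primary safety analysis: "proportion (with 95% CI) with any adverse events in aerosol group and in subcutaneous group". The protocol defines no separate safety set.
- Protocol 11.1.1, secondary analysis set: "intent-to-treat analysis (all infants randomized, analysed in the group to which they were allocated, irrespective of intervention received", for primary and secondary outcomes. SAP 11.3 likewise keeps all participants in their randomised group.
- SAP 11.4, the as-treated safety set: it "includes all children vaccinated, according to the route of vaccination that they received and with at least one safety assessment". It makes no exception for SAEs or withdrawal.
- SAP 11.2, the per-protocol set for the primary immunogenicity analysis: children with an interpretable day-91 sample and no major protocol deviation. The list of deviations includes "Study participant should have been withdrawn during study but was not".
- Protocol 12.1.3, interim safety look: "the DSMB will use data from the first 100 children in each arm to complete 91 days of follow up". SAP 14.0 describes the same look as using the first 100 children per arm and events within 91 days, with no condition of completing follow-up.

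SAP 4.0 tells the statistician to follow both the protocol and the SAP. Neither document ranks one above the other.

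**The concern.** The vaccine is a single dose given under observation, and 7.3 keeps the withdrawn child in clinical follow-up. What withdrawal changes, as written, is therefore the use of that child's data. A rule that takes children out of an analysis because they had a serious event cannot stand beside a primary safety outcome that counts serious events.

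Two analysts could each follow approved text and report different SAE counts. If serious events differed by route, the literal reading would hide the difference in a trial meant to support licensure.

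The same clause reaches the non-inferiority analysis. Being excluded because of an SAE is a post-randomisation event that may depend on route, and it can discard a valid primary-outcome measurement.

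**Working it through.** **1. Reproduce the plan's precision figure.** Protocol 11.2.2 and SAP 8.2 give an upper 95% limit of 0.37% for no events in 1000. The exact (Clopper-Pearson) limit for 0/n is 1 - 0.025^(1/n). For n = 1000 this is 0.368%, and for n = 800 it is 0.46%. Both agree, so the exact method is used below.

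**2. SAE rate under the two readings.** The documents give no expected SAE rate, so a range is assumed, with 1000 vaccinated per arm.

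| Assumed SAE rate | SAP 11.4: SAE children kept | 7.3 applied literally to safety |
|---|---|---|
| 0.5% | 5/1000 (0.16-1.16%) | 0/995, upper limit 0.37% |
| 1% | 10/1000 (0.48-1.83%) | 0/990, upper limit 0.37% |
| 2% | 20/1000 (1.23-3.07%) | 0/980, upper limit 0.38% |
| 5% | 50/1000 (3.73-6.54%) | 0/950, upper limit 0.39% |

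The right-hand column hardly moves, because its numerator is zero whatever the true rate.

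**3. Primary safety measure: proportion with any adverse event.** Let a be the true proportion and s the SAE proportion. Removing the SAE children gives (a - s)/(1 - s), a fall of s(1 - a)/(1 - s). With s = 1%:

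- a = 5%: (50 - 10)/990 = 4.0%
- a = 20%: (200 - 10)/990 = 19.2%
- a = 50%: (500 - 10)/990 = 49.5%

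The fall cannot exceed 0.01/0.99, about 1.0 percentage point.

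**4. Primary per-protocol set.** Take a child with an SAE and a valid day-91 sample.

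- If withdrawn, 7.3 excludes the child, although SAP 11.2 on its own terms would keep a child with an interpretable result and no major deviation.
- If not withdrawn, the child meets a listed SAP 11.2 deviation. Whether that excludes depends on whether it counts as major, which is not defined.

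So either route can remove the child, and neither is certain to.

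As an extreme bound, take the plan's 800 analysed per arm and 90% seropositivity (720/800), with 1% SAEs (8 children) removed from each arm. If all 8 removed from aerosol were seronegative and all 8 from subcutaneous seropositive, the arms become 720/792 = 90.9% and 712/792 = 89.9%. That is an artificial difference of 1.0 point against the 5-point margin. Realistic effects would be smaller.

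**5. Interim set.** A child who dies or leaves before day 91 cannot be among the first 100 to complete under protocol 12.1.3, but can be among the first 100 under SAP 14.0.

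**The case against.** A reader might infer that the planned safety result is emptied of serious events. The documents do not support that. SAP 11.4 is the only dedicated safety set, and it keeps these children. SAP Tables 13.2.1A and B have an SAE column by time window for each arm, Table 14.0.3 Part 3 tabulates SAEs by arm, and Table 11.12.5.3 counts SAEs and deaths among reasons for discontinuation. These tables would make no sense if SAE children were dropped. This objection stands, and it reduces the point to a contradiction. It does not remove it, because 7.3 is current text, SAP 11.4 neither mentions nor overrides it, and both documents bind.

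A reader might also infer that the upper safety limit is understated about five-fold (1.83/0.37 = 4.9). That ratio concerns an SAE-only rate under the literal reading at one assumed rate. It does not describe the primary any-event proportion. Nor would dropping SAE children lead to a report of no reactions: protocol 4.3.2 expects fever in 5-15% of subcutaneous vaccinees.

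On immunogenicity, it is fair to say that SAP 11.2 excludes only for major deviations, that its list also holds clerical items such as CRF labelling, and that the ITT analysis keeps everyone. Per-protocol loss is therefore possible, not stated for every case.

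On the interim look, protocol 8.7.3 and 8.7.6 send all SAEs to the DSMB separately, with notification no later than 7 days after the focal point learns of them, and the DSMB receives quarterly summaries. It would not be unaware of these events. Only the interim denominator is left inconsistent.

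**Conclusion.** The concern holds as an unreconciled contradiction. Protocol 7.3 excludes children withdrawn for an SAE from an unspecified analysis, against protocol 6.2.2.1, protocol 11.1.1 and SAP 11.4, with no rule of precedence.

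Its effect depends on the reading. Under SAP 11.4 nothing is lost. Under a literal 7.3 applied to safety, the SAE count is zero in both arms whatever the true rate, while at an assumed 1% SAE rate the any-event proportion falls by no more than about one point. For the primary per-protocol set, SAE children with valid day-91 samples may be lost; at the same assumed rate even the extreme bound is about one point against the 5-point margin. The interim mismatch is minor.

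All of these sizes rest on assumed SAE rates, because the documents give none. Whether an SAE should lead to withdrawal is a clinical matter and is not judged here.

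**What to change.** - **Protocol 7.3:** delete the closing words that exclude withdrawn children from the analysis. State instead that their data stay in the as-treated safety set and the ITT set, unless consent to use the data is withdrawn, and that an SAE alone is not a reason for exclusion from the per-protocol set.
- **SAP 11.2:** qualify the deviation for children who should have been withdrawn but were not, so that it does not exclude a child when the only trigger is an SAE.
- **Protocol 12.1.3 and SAP 14.0:** use one definition of the interim safety set, namely the first 100 children vaccinated in each arm, with all data to day 91 or to exit if sooner.

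The withdrawal criterion itself is left as it is. The cost is wording in the protocol and SAP, with no new data or visits. The changes should be settled before database lock.

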8.1 Treatments to be administered

8.2 Aerosolized measles vaccine

A dose of measles vaccine, reconstituted for aerosolisation, containing at least 1,000 CCID50 and administered by Nektar/Aerogen nebulizer over 30 seconds, as described in SOP NEK 2/1.

The vaccine and nebulizers will be used and maintained according to the manufacturer specifications, as described in SOP NEK 2/1.

8.3 Subcutaneous control

A dose of measles vaccine (0.5ml), reconstituted for subcutaneous administration, containing at least 1,000 CCID50 and administered as described in SOP WHO 6/1.

The vaccine will be used and stored according to the manufacturer specifications as described in SOP WHO 6/1.

8.3.1 Concomitant medications

Subjects may take all other medications (including rescue medications) as indicated, in line with current Indian MOHFW Guidelines.

Monitoring subject compliance with use of investigational product

Due to the single-dose regime used in this trial, subjects will not be monitored for compliance with dosing schedules as they would be in multiple-dose regimes or those where medications are self/parent/guardian administered. Vaccine administration will occur under direct observation from trial staff for each participant.

8.4 Methods for the trial

8.4.1 Community approval

The trial study area covers more than 150 villages. Preliminary visits will be made to all villages before starting recruitment. Village leaders, influential village residents and other gram panchayat (village level local self government members) will be consulted and asked for verbal agreement for the trial to take place in their village. A written record of meetings will be kept.. Local health providers (family doctors, private clinics, and private doctors) will also be informed of the trial and its purposes.

8.4.2 Enumeration of potential study participants

The method of enumeration will depend on the study area:

- For Vadu, an initial tentative list of all eligible children aged 6 to 10 months will be obtained from the Demographic Surveillance System, Vadu.
- For the other study areas, the study field worker will obtain a list of all eligible children aged 6 to 10 months from local health workers. For full details of this process, please see SOP VAD 3/1. These lists will be in a non-electronic form initially, but in the course of recruitment, details of potential participants will be recorded electronically.

Field workers will visit the parents/guardians of potential participants 2-4 weeks before the infant is 9 months old (Visit 1, see below).

Parents/guardians will be encouraged to consult peers, community leaders and other parents who are study participants. In addition, advertisements about the trial will be displayed in prominent places like gram panchayat offices, temples, and schools in the village.

Parents attending clinics for the vaccination of their child prior to nine months of age (e.g. DPT vaccination at 4 months), will also be given information about the trial.

8.4.3 Vaccination day procedures

The procedures for this visit (Visit 2) are summarized below and described in detail in SOP VAD 4/1.

8.4.4 Follow up schedule

The content of each home or clinic visit shown is described below. The procedures to be followed at each visit are described in SOP VAD 5/1 (home visit and clinic visit).

Activity	Pre-study		Main study									Long term follow up				
	ALL INFANTS		ALL INFANTS							S	SUB-SAMPLE INFANTS [†]					
Day	-14	0	3	7	10	14	17	21	28	56	pre- 91	91	182	252	pre- 364	364
Visit number	1	2	3	4	5	6	7	8	9	10	11	12	13	14	15	16
Home visit with trial information	X							4								
Clinic visit for eligibility, randomization and vaccination		X				Annald				4	>					
Home visit for AE monitoring			x	x	x		x	x	x	x			X	X		
Reminder visit (AE, serology)		A			x			x			x				X	
Clinic visit for AE examination		x	₹ 	A		x			X¥			x				X
Clinic visit for immunogenicity		X							X¥			X				X
Measles surveillance - case based and outbreaks	X	X							X							
Active surveillance for SAE	X	X						Х								

	Table 7:	Timetable o	of home and	clinic v	isits for an	individual	trial participant
--	----------	-------------	-------------	----------	--------------	------------	-------------------

Legend:

AE Adverse event

SAE Serious adverse event

X Procedure undertaken at this time

¥ Only subset – random sample from children in Vadu area

Only subset – random sample from children in Vadu area

